### ***Study Description:***

We plan to enroll approximately 900 adults with moderate to severe TBI who are discharged from inpatient rehabilitation at one of six participating TBI Model Systems sites (WA, NY, PA, TX, OH, IN). Eligible patients will be recruited, consented and randomized into one of two treatment groups. We plan to enroll approximately 607 caregivers.

Randomization will be blocked on study site and discharge to another facility vs. home/community.

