### **STUDY DESIGN OR APPROACH (Criterion 3)**

A 1:1 randomized controlled trial design will compare the effectiveness of two established methods of managing transition from IRF discharge to the next phase of care, stratifying by site and discharge to another facility (e.g., skilled nursing facility) vs. discharge to home/community. We are stratifying on discharge destination based on the relatively lower frequency of discharge to facility (22% across all 6 TBIMS sites in 2015). However, we chose to include discharge to facility for inclusiveness and because our stakeholders encouraged it. For example, we heard "*It would be nice to have an extra advocate*" from a focus group member whose family member was discharged to a skilled nursing facility and experienced poor follow-through of rehabilitation recommendations.

Reporting of the results will follow the CONSORT guidelines (**IR-6**). The extent to which a study design is explanatory vs. pragmatic lies along a continuum, which Tosh and Thorpe have operationalized into evaluation tools. Using the Pragmascope tool, which is an adaptation of Thorpe's PRECIS tool modified for mental health studies, **our study design is highly pragmatic** as determined by the 10-item tool.

For example, our design ensures that our study includes the entire target population and allows for noncompliance based on participant preference. Both interventions are happening in everyday practice in other settings such as in CARF-accredited IRFs and the VHA, and both allow for flexibility based on participant needs and does not require high level expertise of the TBI Care Manager to be delivered. However, our primary outcomes are chosen by our Patient and Family Stakeholders, which will require patient-report and cannot be abstracted from medical records. Our secondary outcomes include objective indicators such as healthcare utilization and unplanned hospital readmissions. We also plan to compensate participants and their caregivers for the time spent to complete our outcome assessments.

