We will explore the effects of the intervention on patient subgroups defined by factors known or hypothesized to have associations with poorer TBI outcome: facility vs. community discharge, race/ethnicity (White, non-Hispanic Black, Hispanic, Other), age (as continuous), male vs. female, lack of or lower degree of caregiver involvement (yes or no), severity of TBI (moderate vs. severe), presence of pre-injury psychosocial limitations (e.g., unemployment, substance abuse, categorized in yes or no) and medical or psychiatric comorbidity (yes or no), as well as study site, resource variability and insurance type (private insurance vs. Medicaid vs. Medicare). These factors will be entered in a single linear regression model in addition to the intervention group, using PART-O-17 as the response variable. Interactions between each factor and the intervention group will be entered in the model and test of interaction will be the test of heterogeneity. Before constructing the model, we will assess whether the explanatory variables (factors) are correlated to each other.

When two or more variables are deemed highly correlated, to avoid problems with collinearity, we will construct the model with the variable that provides the best model (from fit and diagnostic tests).

From previous research, we hypothesize that severity of TBI and presence of pre-injury psychosocial limitations will interact with the intervention group. With our expected sample size, we anticipate being able to address these questions. Some of the factors might not have a statistically significant effect, but have the effect in the expected direction. Effect sizes and confidence intervals will be calculated to express the potential effect of those factors. The results of these analyses will be valuable in designing future studies.

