**Randomization/ Post-Discharge Transition Phase**

After the patient participant has been discharged or after they are consented post-discharge, s/he will be randomly assigned 1:1 into one of two study arms: RDP or RTP. We will stratify randomization on study site and discharge destination (another facility vs. home/ community):

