**Facility**

- nursing home (includes med-center, residential, institutions licensed as hospitals but providing essentially long-term, custodial, chronic disease care, etc.)
- subacute care (includes subacute hospital bed, skilled nursing facility)

The actual act of randomization will be automated via the NDSC BRITE website. Specifically, research staff will click the 'Randomize' button located in the 'Keys' tab of the 'Patient Post-Discharge Information' section under the 'Data' tab once the discharge destination has been entered. The randomization assignment will be automatically recorded in the BRITE website database.

These randomization procedures have been used by our team in prior studies where telephone follow-up was randomly assigned following discharge.

Once randomization occurs, their random assignment will be communicated to the TBI Care Manager (TCM). The TCM will then send out a letter to the patient participant and caregiver (if applicable).

For those who are randomized to the RDP arm, the letter will state that they will be contacted for follow-up at 3, 6, 9 and 12 months post hospital discharge and one year following injury (if applicable).

For those who are randomized to the RTP arm, in addition to a reminder of the follow-up data points as above, the letter will include a reminder of the specific goals of the study and the plan for follow-up calls with the TCM.

The meeting schedule will be modified throughout the intervention time period to fit the needs of both the patient and caregiver participants and may include evening or weekend appointments.

The TCM will also send patient and caregiver participants assigned to the RTP group a brief description of the general role of the TCM as well as a description of the specific TCMs at each site including education and work experience. This form may be mailed with the randomization letter, or part of a subsequent mailing.

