### **Masking (or Blinding)**

This study uses **masked outcome assessment**, which means that staff members who collect outcomes data from both patient and caregiver participants at 3-, 6-, 9- and 12 months must be unaware of patient participants' treatment group allocation. Several procedures are used to help outcomes staff to remain unaware of group assignment.

Randomization will be automated via a NDSC database to minimize unblinding. Specifically, research staff or the TCM will enter discharge destination and study site into the specified NDSC database as part of the discharge destination and date form. Subsequently the TCM will be notified via email of group assignment. Ideally, group assignment will be known only by coordinators and the TCM(s) at a given site, and the data coordinator at Craig Hospital.

In addition, only TCMs will have access to the 'Notes' tab on the NDSC database where adverse events, serious adverse events (SAE), unanticipated problems and note-to-files are entered. The reason is that blinded assessors would be unblinded if they observed entries for these events if entered by a TCM. As a result, all information relating to adverse events, SAEs, unanticipated problems and note-to-files will be sent by blinded assessors to the TCMs at each site for entry into the database.

Other procedures for preventing inadvertent unmasking will be used such as ensuring that data collectors and TCMs are not using office spaces in close proximity while TCMs are contacting patient participants, and minimizing the meetings that data collectors and TCMs attend in

common. Also, data collectors will not have access to the treatment list serve to prevent inadvertent unmasking from that source.

Staff will continue with a post-discharge questionnaire even if unblinded during the questionnaire administration, but will attempt to have another staff member (if available) administer subsequent questionnaires.

We will record on each post-discharge questionnaire any potential unblinding incidents by asking assessors: 1. if they believe they were unblinded during the questionnaire or any previous questionnaire; and 2. to guess which study arm they believe the participant was assigned to.

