**Aim 1, Hypothesis 1:** Both the PART-O-17 and the QoLIBRI measures are numeric with a fairly large range that can be considered as continuous for data analysis. We will test the difference in means for PART-O-17 and QoLIBRI between the two groups at 6-month post-discharge using a two-sided t-test for independent samples. We will also test if the intervention has a long-term effect by comparing the two groups at 12-months post discharge using the same type of t-test.

**Aim 2, Hypothesis 2:** To compare the trajectory of improvement for 3-, 6-, 9- and 12-months post-discharge, we will plot individual trajectories over time and if it appears that the majority of people are leveling off over time we will consider a growth model. Otherwise, we will use a linear mixed model, with the outcome (PART-O-17 or QoLIBRI) as the response variable, and time and other factors (such as age, sex, race/ ethnicity, education, injury severity) as explanatory variables, and add intervention group and its interaction with time to test whether the interventions and time had an effect in the trajectory of the outcome.

**Aim 3, Hypothesis 3:** To compare the healthcare utilization in the first-year post discharge, the two groups will be compared on the distribution of categories of completed planned outpatients visits (less than 50%, between 50 and 75%, and more than 75%) by using a Chi-Square test. Both, the number of urgent care visits and the number of unplanned hospitalizations will be compared by means of a Poisson regression, which will include group and possibly adjusting for other factors (age, sex, race/ethnicity, education, injury severity). A statistically significant coefficient for intervention groups will show that the two groups differ in emergency and unplanned medical visits.

**Aim 4, Hypothesis 4a:** To compare caregiver burden, HRQOL, and satisfaction with roles and activities, we will apply t-tests for difference of means for independent samples for those measures that are found to have a normal distribution. We will also conduct heterogeneity of treatment effects analyses as we planned for other measures.

**Aim 4, Hypothesis 4b:** Using the Bakas Caregiving Outcomes Scale, Zarit Burden Interview, Sf-12, and the PROMIS Satisfaction with Social Roles and Activities for caregivers at 3-, 6-, 9- and 12-month follow-ups as response variables, we will fit a linear mixed model or growth model similar to the ones in hypothesis 2.

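### Aim 1 is tested with an unadjusted t-test although randomisation is stratified by site and discharge destination; adding both factors would give a modest gain in precision at little cost

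*Combined protocol and SAP*

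**What the plan says.** The section Randomization/Post-Discharge Transition Phase states "We will stratify randomization on study site and discharge destination", and the Abstract (Study Description) puts it as "Randomization will be blocked on study site and discharge to another facility vs. home/community". With six sites and two destinations there are 12 strata. No block size or within-stratum method is given.

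Under Data Analysis Plan Specific to Each Aim, Aim 1 compares mean PART-O-17 and QoLIBRI "between the two groups at 6-month post-discharge using a two-sided t-test for independent samples". The long-term effect is tested by "comparing the two groups at 12-months post discharge using the same type of t-test". Neither test has covariates, and both power sections assume the same t-test for PART-O-17.

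Site and destination appear in three other kinds of place, none of which supplies the primary estimate:

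- The heterogeneity sections put both into an exploratory regression with treatment interactions.
- Assessment of Variability of Resources and Processes promises to look at confounding by site, but names no Aim 1 model and does not mention destination.
- The Aim 2 and Aim 3 covariate examples (age, sex, race/ethnicity, education, injury severity) name neither factor.

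**The concern.** A two-sample t-test estimates its standard error as if patients had been allocated without regard to strata. Stratified blocking removes most chance imbalance between arms in the stratum factors. If those factors predict outcome, the treatment estimate varies less than the t-test reports. Confidence intervals are then too wide and p-values too large.

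The plan itself expects destination to matter: the heterogeneity section lists "factors known or hypothesized to have associations with poorer TBI outcome: facility vs. community discharge". Site is listed only as something to explore.

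What is at stake is efficiency and the width of the interval, not bias or false positives. Width matters here because the plan says the p-value should not decide significance alone and that stakeholders will judge the meaningfulness of effects.

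**Working it through.** **The plan's own figure.** Power Analysis claims practically 100% power for an effect size of 0.5 with 500 or more patients. The exact noncentral t gives 0.9999 at N = 500 (two-sided 0.05, 1:1), so this reproduces. Power Analysis Revisited extends the range down to an effect size of 0.3. Its claim of 0.80 power at N = 300 and effect size 0.3 comes out at 0.74, but that is a separate matter and nothing below uses it.

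**Inputs from the documents.** Patients at 6 months: 720 (Appendix 1), i.e. 900 with 80% retention (Table 1, Recruitment/Enrollment Assessment Timeline), so 360 per arm. SD of PART-O-17: 0.75 (Power Analysis). Share discharged to a facility: 22% (Study Design or Approach). Two-sided alpha: 0.05.

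**Assumed input.** R², the share of outcome variance explained by the strata, is not given. I use 0.02, 0.05 and 0.10, with 0.20 as a speculative upper bound. For scale, a facility–community gap of g SD explains 0.22 × 0.78 × g² of the variance: 0.043 at g = 0.5 and 0.084 at g = 0.7. The effect of 0.20 SD is also my assumption; it is smaller than any effect the plan considers.

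**Case 1: allocation balanced within strata.** In SD units:

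- Reported SE = sqrt(4/720) = 0.0745.
- True SE = 0.0745 × sqrt(1 − R²), so the overstatement factor is 1/sqrt(1 − R²).
- True type I error = 2 × [1 − Φ(1.96/sqrt(1 − R²))].
- t-test power = Φ((d − 1.96 × 0.0745)/true SE).
- Adjusted power: noncentral t with effect d/sqrt(1 − R²) and 712 df.
- Random loss partly undoes the balance. With 80% retained, replace R² by 0.8R² in the t-test formulas.

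| R² | SE overstated: exact balance / after loss | Type I error: exact balance / after loss | Power at d = 0.20: t-test → adjusted | Power at d = 0.30: t-test → adjusted |
|---|---|---|---|---|
| 0.02 | 1.0% / 0.8% | 0.0477 / 0.0482 | 0.767 → 0.772 | 0.982 → 0.982 |
| 0.05 | 2.6% / 2.1% | 0.0443 / 0.0455 | 0.771 → 0.785 | 0.983 → 0.985 |
| 0.10 | 5.4% / 4.3% | 0.0388 / 0.0410 | 0.777 → 0.806 | 0.985 → 0.989 |
| 0.20 | 11.8% / 9.1% | 0.0284 / 0.0325 | 0.791 → 0.850 | 0.990 → 0.994 |

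The power columns assume exact balance. After loss, t-test power at d = 0.20 is lower by less than 0.003 at R² = 0.05 and 0.10. The effect detectable with 80% power falls from 0.207 to 0.204 SD at R² = 0.05, from 0.206 to 0.198 at 0.10, and from 0.202 to 0.187 at 0.20.

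**Case 2: allocation not balanced within strata.** The t-test has its nominal 0.05 error rate and adjustment only adds precision. Power at d = 0.20 rises from 0.764 to 0.785, 0.806 and 0.850 for R² = 0.05, 0.10 and 0.20.

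**Interval width, either case.** The reported 95% half-width for PART-O-17 is 1.963 × 0.75 × sqrt(1 − R²) × 2/sqrt(720). This is 0.110 points for the t-test, against 0.107, 0.104 and 0.098 adjusted at R² = 0.05, 0.10 and 0.20.

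**Simulation check of Case 1.** 900 patients were randomised in 12 strata with assumed blocks of 4, and 80% were retained at random.

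- Type I error of the t-test over 92,000 runs was 0.0455 at R² = 0.05 and 0.0402 at 0.10.
- Power at d = 0.20 (12,000 runs each, R² = 0.05, 0.10, 0.20) was 0.773, 0.774 and 0.785 for the t-test, and 0.787, 0.805 and 0.850 adjusted.
- The true SD of the t-test estimate was 0.0735, 0.0714 and 0.0684, against a reported 0.0745. The adjusted estimate had 0.0732, 0.0706 and 0.0668, against a reported 0.0727, 0.0708 and 0.0667.
- In separate runs under the null (4,000 per setting, with full and with 80% retention), the adjusted model rejected in 0.044 to 0.055 of them.

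Under balance, then, adjustment hardly changes the estimate. What it mainly does is report the precision the design already has.

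**The case against.** The strongest reply is that nothing is broken. The t-test is valid, power at the plan's own effects is at least 0.98 with or without adjustment, and every figure for the gain rests on an R² the documents do not supply and on an effect of 0.20 SD that the plan never considers. All of that stands, and it is why this is an improvement and not an error.

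The exact-balance SE figures also flatter the case, because 720 is the number left after loss. The post-loss figures of 2.1% and 4.3% are the fairer ones for this trial. The calculation further credits all stratum variance to additive site and destination terms; a site-by-destination component would not be recovered.

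Timing is the most practical objection. Version 15.0 is dated 01-23-23, and Appendix 1 had 12-month follow-up due for completion by 10/31/2022. The DSMB reviews interview or performance outcomes, and the study statistician may run unblinded analyses for it in closed session. Whether that happened is not known. If arm-level outcomes have been seen, a change of primary model loses credibility.

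Two points carry less weight. The exploratory heterogeneity regression contains site and destination, but with interactions, and it is not the Aim 1 test. The Manual of Procedures, which is to hold randomisation and analysis procedures, may settle the block size, but it does not alter the t-test that the plan states.

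**Conclusion.** The point holds as a modest, conditional improvement. The plan stratifies by two factors, expects one of them to be associated with outcome, and leaves both out of the primary comparison. If the strata are balanced and explain 5% to 10% of variance, the t-test's standard error is about 2% to 5% too large, its true error rate is about 0.04 to 0.046, and adjustment adds 0.014 to 0.029 of power at 0.20 SD. If they are not balanced, the t-test is at its nominal level and adjustment adds 0.021 to 0.042. At R² of 0.02 or less the difference is negligible, and at effects of 0.3 SD or more it does not change the power conclusion. The size rests on the assumed R², random loss and, for the simulation, blocks of 4. The direction does not depend on those particular values, provided the strata predict outcome.

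**What to change.** In the Aim 1 text, define the primary analysis of PART-O-17 and of QoLIBRI at 6 months, and the 12-month comparison, as a linear model of outcome on arm with fixed effects for site (six levels) and discharge destination (two levels). Report the unadjusted t-test as a supporting analysis. Put the same two factors in the Aim 2 mixed model and in the imputation model, so that imputation and analysis agree.

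Both factors are available for every randomised patient: under Masking, "research staff or the TCM will enter discharge destination and study site into the specified NDSC database" before the assignment is sent out, and the randomise step is taken "once the discharge destination has been entered".

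The cost is a wording change and six degrees of freedom (five for site, one for destination) out of about 720; no new data are needed. State the block size and method at the same time. Date the change before outcomes are examined by arm, and say whether any unblinded outcome analysis has already been run for the DSMB. If outcomes have been examined by arm, keep the t-test as primary and report the adjusted model as a labelled sensitivity analysis.

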### **Data Sources and Resources (IR-1)**

Data collected as part of the national longitudinal TBIMS database during inpatient rehabilitation and at 12-months post-injury will be available for the majority of participants in the proposed study. These uniform data elements will be collected from individuals who are not enrolled in TBIMS but who enroll in the current study to ensure consistency. TBIMS data elements include demographic variables, information about pre-injury social history, detailed data on injury type and severity, and functional status at rehabilitation admission and discharge (<https://www.tbindsc.org/Syllabus.aspx>).

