### **Power Analysis**

As can be seen in the Recruitment/Enrollment table above (p. 26), we expect to enroll a minimum of 300 individuals per year for 3 years (total N = 900). We based our power calculation on the PART-O-17, the primary outcome for which we have the most relevant data in TBI. Unpublished data from a sample discharged from inpatient TBI rehabilitation showed a PART-O-17 Total (which can range from 0 to 5) average score of 1.51 (SD=0.65) at 3-months follow-up and 1.66 (0.72) at 9-months follow-up (publication in preparation). Minimal detectable differences (MDD) were 0.57 and 0.63 at 3 and 9 months, respectively. Using these results, we calculated the power of finding a difference of 0.60 (average of the two MDDs) between the two groups under various assumptions as follows:

Test: t-test for independent samples, two-tailed, allocation ratio=1

[figure not shown]
Significance level=0.05

Common standard deviations: 0.75 (higher than the observed in previous studies to be conservative)

Mean PART-O scores (Intervention mean minus control mean): The minimal detectable difference of the instrument is 0.6. To be more conservative, we started the difference between the two means at 0.4. Assuming SD=0.75 (in the higher side of previous studies) the calculated effect size based on this mean and SD is 0.5333. Therefore, we used values of 0.5 to 0.8 by increments of 0.05 for the effect sizes.

[figure not shown]
Sample sizes: from 500 to 900 individuals (by 100)

The graph shows that even with an effect size of 0.5 (corresponding to a difference of 0.4 points between the two groups and under an SD larger than those observed in prior studies), we have practically 100% power to detect the difference between the two groups with sample sizes of 500 and above (we expect to have 900).

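### The primary 6- and 12-month comparisons are unadjusted t-tests, although baseline factors that the protocol itself links to outcome or uses as covariates are planned for collection from all patients, so some precision is given up

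*Combined protocol and SAP*

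**What the plan says.** Under Data Analysis Plan Specific to Each Aim, Hypothesis 1 compares both primary outcomes "between the two groups at 6-month post-discharge using a two-sided t-test for independent samples". The longer-term effect is tested by "comparing the two groups at 12-months post discharge using the same type of t-test". No covariate enters either test, and neither do the randomisation strata, site and discharge destination.

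No adjusted version of the Aim 1 main effect appears elsewhere:
- The adjusted repeat under Power for Secondary Outcomes concerns the healthcare-utilisation counts.
- The multi-factor regression on PART-O-17 is the heterogeneity analysis.
- The COVID-19 model is a follow-on analysis.

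For the same two outcomes, the Aim 2 linear mixed model takes "time and other factors (such as age, sex, race/ ethnicity, education, injury severity) as explanatory variables". The heterogeneity section lists older age, greater injury severity and pre-injury psychosocial limitations, with unemployment as an example, among factors known or thought to go with poorer outcome.

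On availability, Data Sources and Resources says that the TBIMS elements include demographics and "information about pre-injury social history, detailed data on injury type and severity, and functional status at rehabilitation admission and discharge". The same elements are to be collected from patients outside TBIMS. Descriptive/Demographic Variables lists age, years of education, pre-injury employment and inpatient functioning. The baseline sections include no PART-O-17 or QoLIBRI measurement.

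**The concern.** With no baseline value of either outcome, the usual route to a tighter estimate is closed. What remains is prognostic information describing the patient before randomisation. The plan intends to hold that information and uses part of it in Aim 2, but leaves it out of the comparison on which the trial will be judged. Outcome variance that age, education, employment, severity and discharge function could explain then stays in the error term. At stake are the width of the primary confidence interval and the power to detect a modest effect. The second matters here because the stakeholders reported under Primary Outcomes regarded even small gains as important.

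**Working it through.** **Inputs.** The Power Analysis specifies "Test: t-test for independent samples, two-tailed, allocation ratio=1" and "Significance level=0.05", with an SD of 0.75 for PART-O-17. On the effect, it says "we started the difference between the two means at 0.4", so d = 0.4/0.75 = 0.533, and its graph begins at 0.5. The 2019 revisit goes down to 0.3. Recruitment Table 1 plans 900 patients and 80% retention, and the milestone schedule gives 720 completed 6-month follow-ups (900 × 0.80). R-squared, the share of outcome variance explained by the baseline variables, is **an assumption**: the documents give none.

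**Step 1: the plan's own figure.** Power = Φ(d·√(N/4) − 1.960). At N = 500 and d = 0.5 this is Φ(5.590 − 1.960) = 0.9999, so the claim of practically 100% reproduces. At N = 720, d = 0.5 gives over 0.9999 and d = 0.3 gives Φ(4.025 − 1.960) = 0.981. (The revisit's claim of 0.80 power with 300 patients at 0.3 SD does not reproduce; the two-sided value is 0.738. That is a separate matter and nothing here rests on it.)

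**Step 2: effect of adjustment at N = 720.**
- SE = 0.75·√(1 − R²)·√(4/720); unadjusted 0.0559 points
- 95% half-width = 1.96 × SE
- Equivalent N = 720/(1 − R²)
- Detectable d at 80% power = (1.960 + 0.842)·√(1 − R²)·√(4/720)

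| Assumed R² | SE ratio | 95% half-width (points) | Equivalent N | Detectable d | Power, d = 0.2 | Power, d = 0.3 |
|---|---|---|---|---|---|---|
| 0 (as planned) | 1.000 | 0.1096 | 720 | 0.209 | 0.765 | 0.9805 |
| 0.10 | 0.949 | 0.1039 | 800 | 0.198 | 0.807 | 0.9888 |
| 0.20 | 0.894 | 0.0980 | 900 | 0.187 | 0.851 | 0.9945 |
| 0.30 | 0.837 | 0.0917 | 1,029 | 0.175 | 0.894 | 0.9978 |

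An R² of 0.05 would cut the standard error by only 2.5% (√0.95 = 0.975). At d = 0.5, power exceeds 0.9999 in every row. An effect of 0.2 SD is 0.15 PART-O-17 points.

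**Step 3: QoLIBRI.** The documents give no SD or power calculation for it, and proxies do not complete it, so its analysed number will be below 720. The SE ratios apply at any N; the power figures do not carry over.

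**Step 4: which variables the plan itself supports.** Aim 2 names age, education and injury severity (with sex and race/ethnicity) as examples. Pre-injury unemployment appears in the heterogeneity list. Discharge function is in neither list but is planned for collection. Randomisation follows discharge, so all of these describe pre-randomisation status.

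**The case against.** The strongest reply is that the trial does not need the precision: power is about 98% at 0.3 SD and over 99.9% at 0.5 SD without adjustment, and 0.2 SD is an effect the plan never uses. That stands as regards the plan's chosen effects. It does not cover confidence-interval width, small effects, or QoLIBRI, for which nothing was calculated.

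Several stronger readings are tempting, and the documents do not support them:
- **That the primary result would be biased or exposed to chance imbalance.** Randomisation makes the t-test unbiased, and its error rate already allows for imbalance. With 360 per arm, a standardised covariate difference has a standard error of √(2/360) = 0.075 SD.
- **That the predictors are strong.** Associations are described only in words.
- **That complete data are on file for every patient before randomisation.** Collection is planned for all, but patients are asked to supply the demographics, consent may follow discharge, and the Data Quality Guidelines allow medical abstraction for non-TBIMS patients to be entered up to three months after randomisation.
- **That Aim 2 already uses the full set.** It does not name pre-injury employment or discharge function.
- **That Aims 1 and 2 would give conflicting month-6 effects.** Aim 2 tests arm by time, not a month-6 contrast, and a shared list would not make the two models agree.
- **That missing covariates are dropped in the main analysis.** Imputation is the main approach; removal of the covariate belongs to the sensitivity analysis.

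**Conclusion.** The point holds as a matter of efficiency. Both primary outcomes are tested without adjustment at 6 and 12 months, no adjusted main-effect analysis is planned, and relevant baseline data are to be collected anyway. For PART-O-17, under an assumed R-squared of 0.10 to 0.30 and 720 completers, the half-width of the interval falls from 0.110 to between 0.104 and 0.092 points, and power at 0.2 SD rises from about 76% to 81-89%. These figures treat the completers as the analysis set, whereas the plan intends multiple imputation where the missingness mechanism allows it. The t-test is valid, and at the plan's own effect sizes the change would hardly affect power. It should be made, but the trial's validity does not depend on it.

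**What to change.** Before unblinded outcome data are analysed, define the primary analysis of PART-O-17 and QoLIBRI at 6 and 12 months as a linear model of outcome on:
- arm;
- the stratification factors, site and discharge destination;
- a short fixed list describing pre-randomisation status: age, education, pre-injury employment, one injury-severity measure and functional status at discharge.

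Choose a severity measure available for nearly all patients. Duration of post-traumatic amnesia is a doubtful choice, because patients may be enrolled before they emerge from it. Impute missing covariate values without using outcome or arm, or use a missing category, and delete the sensitivity rule that removes the covariate. Keep the unadjusted t-test as a sensitivity analysis. Replace the open-ended examples in Aim 2 with the same list.

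The cost is a short SAP amendment, with no new data or visits. The amendment must be dated and must state who had seen outcomes by arm: version 15.0 (January 2023) postdates the scheduled end of 12-month follow-up (October 2022), and the DSMB closed session allows the study statistician to run unblinded analyses.
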